Vieira Rosa et al. (2024) conducted a systematic review and meta-analysis including 14 articles from 12 randomized controlled trials that compared general and specific exercises for chronic mechanical neck pain. The review found no significant differences in pain intensity between aerobic and specific exercises in the medium term (MD 0.95, 95% CI -1.62 to 3.51) or long term (MD 0.32, 95% CI -1.05 to 1.68) (Vieira Rosa et al., 2024). Similarly, mind-body exercises were not superior to specific exercises for reducing pain in the medium (MD 0.54, 95% CI 0.00 to 1.08) or long term (MD 0.06, 95% CI -0.59 to 0.46) (**Vieira Rosa et al., 2024**). Functional disability outcomes also showed no significant differences between groups in both the medium (MD 0.01, 95% CI -0.25 to 0.27) and long term (**Vieira Rosa et al., 2024**). The review concluded that although both exercise types may provide benefit, the quality of evidence remains very low to low, indicating a need for high-quality RCTs (**Vieira Rosa et al., 2024**).

Several individual studies included in the meta-analysis echoed these findings. **Iversen et al. (2018)** observed modest improvements in both groups, with no significant differences in pain or disability. Similarly, **Lauche et al. (2016)** found comparable effects between tai chi and neck-specific exercises in reducing symptoms over 12 weeks.

CHAPTER III

SUBJECTS AND METHODS

Study Design

This study will be a randomized controlled trial (RCT) conducted to compare the effects of body mind exercises (mindful aerobic exercises), specific neck exercises and combined (body mind and specific) exercises in addition to conventional therapy on neck pain severity, functional disability, neck range of motion, isometric neck muscle strength and quality of life in patients with chronic mechanical neck pain.

The study will follow CONSORT guidelines for randomized trials and will be conducted at the outpatient physical therapy clinic of the Faculty of Physical Therapy, Cairo University.

Ethical approval will be obtained from the institutional review board (IRB) of the Faculty of Physical Therapy, and the trial will be registered on ClinicalTrials.gov before patient enrollment.

Sample Size Calculation

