Sample size was calculated using **G*Power software version 3.1.9.7**, referencing effect size data from a recent RCT comparing general and specific exercises in neck pain (**Vieira Rosa et al., 2024**). A priori power analysis for a repeated measures ANOVA (within-between interaction) was used with an effect size of 0.25, alpha level (α) = 0.05, and power ($1-\beta$) = 0.95. The estimated sample size required was **76 participants**, which was increased to account for potential dropouts as shown in (**Figure 1**). Thus, the total sample will include **80 patients**, randomly allocated into four equal groups ($n = 20$ per group):

- **Group A:** Conventional therapy.
- **Group B:** Conventional therapy + Body mind exercises (mindful aerobic exercise).
- **Group C:** Conventional therapy + specific neck exercises (cervical and scapular stabilization exercises)
- **Group D:** Conventional therapy + combined (body mind and specific) exercises

[figure not shown]

Figure 1 sample size calculation

Patients

A total of 80 patients (50-65 years old) with chronic mechanical neck pain will be recruited from outpatient orthopedic and physical therapy clinics. All participants will provide written informed consent prior to enrollment.

Inclusion Criteria (Daher et al., 2021)

- Adults aged between 50-65 years
- Diagnosis of chronic mechanical neck pain (pain duration ≥ 3 months)
- Pain intensity of at least 3/10 on the NPRS

Exclusion Criteria

- History of cervical surgery
- Specific neck conditions (fractures, neoplasm, infection)
- Pregnancy
- Severe cardiopulmonary disease or other systemic illness affecting participation

Randomization and Blinding

Participants will be randomly allocated into four groups using a computer-generated block randomization method. Allocation concealment will be ensured using sealed opaque envelopes. The **outcome assessor** will be blinded to group allocation.

Outcome Measures

All outcomes will be measured at **baseline (pre-intervention)** and after **6 weeks (post-intervention)**.

1. Pain Intensity

Measured using the **Arabic version of the Numeric Pain Rating Scale (NPRS)**, which has been validated for Arabic-speaking populations (**Alghadir et al., 2016**). Patients will be asked to rate their neck pain intensity on a scale from 0 (no pain) to 10 (worst possible pain).

2. Functional Disability

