6	Maintaining chin-tuck position plus unilateral and bilateral upper extremity with an external load of 500 ml full water bottle and reciprocal lower extremity movements in supine, prone, quadrupedal, and standing positions	15 s	12 times

Figure 3 *progression of cervical stabilization exercises adopted from Oz HE et al., (2024).*

Scapular stabilization exercises:

The Scapular stabilization exercises will be comprised of four exercise programs. The participants sat on the knees in 90° flexion position, and a Swiss ball was propped up between the chest and stomach. Looking from the side, the earlobe, acromion of scapula, and pelvis made a straight line (**Kang et al., 2021**).

A. Scapula retraction exercise: While retracting both the scapula, raise both the arms backward.

B. Scapula mobilization exercise: With thumbs up, raise both the arms sideways making a straight line with the shoulders.

C. Scapula dynamic stabilization exercise I: Raise one arm beside the ear and push out the other arm behind the back. Do the same for the opposite side.

D. Scapula dynamic stabilization exercise II: Raise both the arms beside the ears and then push them down bending and maintaining elbows at 90°. Raise both the arms beside the ears again and put them down.

Each exercise was performed with two sets of 15 reps, 10 sec per rep as shown in (Figure 4).

Figure 4 scapular stabilization exercises adopted from Kang et al., (2021).

Group D : Combined exercise group.

Group D will receive **conventional therapy in addition to mindful aerobic exercises, cervical and scapular stabilization.**

Statistical analysis:

Data will be analyzed using **SPSS version 27** (IBM Corp, Chicago, IL, USA). Descriptive statistics (mean \pm SD) will be reported for all variables. Normality of distribution will be assessed using the **Kolmogorov–Smirnov test**. **Within-group comparisons** (pre vs post) will be conducted using **paired t-tests**. **Between-group differences** will be analyzed using **one-way ANOVA** followed by **post hoc Tukey’s test**. The level of significance will be set at **p < 0.05**.

REFERENCES

- Alagingi NK. Chronic neck pain and postural rehabilitation: A literature review. *Journal of Bodywork and Movement Therapies*. 2022 Oct 1;32:201–6.
- Algarni, A. S., Ghorbel, S., & Jones, J. (2014). Validation of an Arabic version of the Neck Disability Index in patients with neck pain. *Spine*, 39(19), E1135–E1140.

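### The sample size is set on a group-by-time interaction at effect size 0.25, but the analysis names a one-way ANOVA with Tukey's test, the scale of 0.25 is not stated, and its source is misdescribed

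*Protocol*

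**What the plan says.** Protocol, Chapter III, Sample Size Calculation: "A priori power analysis for a repeated measures ANOVA (within-between interaction) was used with an effect size of 0.25", at alpha 0.05 and power 0.95. The result is given as: "The estimated sample size required was 76 participants, which was increased to account for potential dropouts". The total becomes 80, in four arms of 20. The effect size is introduced as "referencing effect size data from a recent RCT comparing general and specific exercises in neck pain".

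Protocol, Chapter III, Outcome Measures: there are two assessments, at baseline and at 6 weeks.

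Protocol, Chapter III, Statistical analysis: within-group change is tested by paired t-tests. For the arms, "Between-group differences will be analyzed using one-way ANOVA followed by" Tukey's post hoc test. No repeated-measures or mixed ANOVA is named, and the variable entered in the one-way ANOVA is not stated.

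Protocol, Chapter II, Comparative Studies: the publication cited for the effect size is described there as a systematic review and meta-analysis of 12 randomized trials. On pain, "The review found no significant differences in pain intensity between aerobic and specific exercises in the medium term".

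**The concern.** The procedure used to size the trial is not the one named for the analysis, and an effect size of 0.25 does not mean the same thing in both. In a one-way ANOVA, f = 0.25 is the usual medium effect. In the interaction procedure with two time points and correlation 0.5, the same number stands for a treatment effect twice as large. A reader who takes 0.25 at face value will believe that the trial can almost certainly detect medium differences between arms.

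This matters most if the result is null. All eleven hypotheses are worded as no significant difference. A non-significant result from a trial advertised at 95% power would be taken as support for them, although differences of 0.5 to 0.8 SD between two arms would usually be missed. The source given for 0.25 does not help the reader, because it is labelled as one kind of study in one chapter and another kind in the next.

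**Working it through.** **Inputs.** From the protocol: k = 4 arms, m = 2 time points, effect size 0.25, alpha 0.05, power 0.95, N = 76 raised to 80, n = 20 per arm. Assumed: correlation rho = 0.5 between baseline and week 6, and no sphericity correction (none is needed with two time points). The correlation may be shown in Figure 1, which is not available here.

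**1. Reproduce 76.** For the within-between interaction, lambda = f² × N × m / (1 − rho), with (k − 1)(m − 1) = 3 and (N − k)(m − 1) = N − 4 degrees of freedom.
- N = 76: lambda = 0.0625 × 76 × 2 / 0.5 = 19.0, power 95.9%.
- N = 72: lambda = 18.0, power 94.8%.
- N = 80: lambda = 20.0, power 96.8%.

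So 76 is the smallest multiple of four that reaches 95%. Other correlations give a different N: 144 (rho 0), 104 (0.3), 60 (0.6) and 48 (0.7). Of the values tried, only 0.5 gives 76.

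**2. Translate 0.25 to the one-way scale.** For a one-way ANOVA, lambda = f² × N with 3 and N − 4 degrees of freedom. Setting the two equal at rho = 0.5 gives f² = 0.0625 × 2 / 0.5 = 0.25, so f = 0.50. With equal baselines, the four arm means at week 6 then have an SD of 0.5 outcome SD. What this means for the extreme arms depends on the pattern:
- two arms at −0.5 and two at +0.5: 1.0 SD apart;
- one arm at −a, two at 0, one at +a: a²/2 = 0.25, so a = 0.71 and the extremes are 1.4 SD apart.

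**3. Power of the named F test with N = 80.**

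| Reading of 0.25 | One-way f | lambda | Power |
|---|---|---|---|
| Interaction scale, rho 0.5 | 0.50 | 20.0 | 96.8% |
| Conventional one-way f | 0.25 | 5.0 | 42.0% |

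At N = 76 the second row is 40.0%. On that reading, 80% power would need 180 patients and 95% would need 280.

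The first row holds for week-6 scores at any correlation. For change scores, the same effect has 88.6% power at rho 0.3, 96.8% at 0.5 and 99.9% at 0.7. A simulation of 20,000 trials at rho 0.5 gave 97.0% on week-6 scores and 96.9% on change scores for the full effect, and 41.9% and 42.2% for half of it.

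**4. What 80 patients can detect.** For week-6 scores, or change scores at rho 0.5 (where the SD of the change is SD × √(2 × 0.5) = SD), the F test has 80% power at f = 0.38 and 95% at f = 0.48.

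For Tukey pairs, the critical t is 2.627 on 76 degrees of freedom and the noncentrality is d × √(20/2).

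| Difference (SD) | Noncentrality | Power for that pair |
|---|---|---|
| 0.5 | 1.58 | 16% |
| 0.8 | 2.53 | 47% |
| 1.0 | 3.16 | 70% |
| 1.4 | 4.43 | 96% |

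**5. Source.** Chapter III calls the reference a single RCT. Chapter II and the reference list give the same citation as a systematic review and meta-analysis. None of the results quoted from it in Chapter II is an f of 0.25.

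**The case against.** The strongest reply is that the stated power is correct for the effect that was put in. With two time points, the interaction F test is the same test as a one-way ANOVA on change scores. The Statistical analysis section leaves the variable open, and a separate analysis plan may define it. If change is analysed, the sized test and the planned test coincide. Even on week-6 scores, the one-way ANOVA keeps 96.8% power for the assumed effect. This stands, and it rules out three stronger readings.

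- A reader might infer that power has fallen from 95% to 42%. Those two figures belong to two different treatment effects that share the label 0.25. The change of test alone costs nothing on the overall F test at correlation 0.5. The 42% applies only if the authors meant a conventional one-way effect, and the text does not say so.
- A reader might infer that the trial is sized on a test it will never run. The protocol supports only that it does not name that test.
- A reader might infer that the protocol's own evidence refutes the assumed effect, since the pooled pain differences it quotes are 0.06 to 0.95 in absolute size. At an assumed SD of 2 points (range 1.5 to 2.5), the largest is 0.95 / 2 = 0.48 SD (0.38 to 0.63). But no SD is given, and those figures compare general with specific exercise. They do not cover conventional therapy alone or the combined arm, which also enter the four-group test.

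The reply does not remove the mismatch between the two sections, the missing scale and meaning of 0.25, or the wrong label on the source.

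**Conclusion.** The point holds as a mismatch between sizing and analysis, and should be fixed. The number 76 is not an arithmetic error. It reproduces under an assumed correlation of 0.5 that could not be checked against Figure 1.

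The stated 95% holds only for a one-way f of about 0.50, with extreme arms about 1.0 to 1.4 SD apart, and the protocol does not say this. Depending on how 0.25 is read, the named F test has about 97% or 42% power with 80 patients. The pairwise Tukey comparisons, which separate the exercise types, have 16% to 47% power at 0.5 to 0.8 SD and 70% at 1.0 SD. Left unqualified, the power statement therefore does not tell a reader what the named tests can detect. The description of the source contradicts the protocol's own account, whatever view is taken of the power.

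**What to change.** Keep 80 patients and change the wording in three places.

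1. In Statistical analysis, name the variable entered in the between-group test. A one-way ANOVA on change scores is exactly the sized interaction test. A baseline-adjusted ANCOVA is an alternative, provided its assumed correlation is stated and the power is given for that model.
2. In Sample Size Calculation, replace the unqualified claim of 95% power at 0.25 with what the chosen test can detect. For a one-way ANOVA on week-6 scores, or on change scores at correlation 0.5, this could read: *With 20 patients per arm, the four-group F test has 80% power at f = 0.38 and 95% at f = 0.48. A Tukey pairwise comparison has 16%, 47%, 70% and about 96% power for differences of 0.5, 0.8, 1.0 and 1.4 SD.* If 0.25 is kept, state that it is on the interaction scale, give the correlation, and say that it corresponds to a one-way f of 0.50.
3. Describe the cited source as the systematic review and meta-analysis that it is, and state where 0.25 comes from.

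The cost is protocol wording only, with no extra patients. The downside is that the stated power will look less favourable.

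### Within-arm paired t-tests share the p < 0.05 threshold with the between-arm ANOVA and are not ranked below it, although no hypothesis concerns change within an arm

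*Protocol*

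**What the plan says.** The Statistical analysis section of Chapter III names two sets of tests. The first is within each arm: "Within-group comparisons (pre vs post) will be conducted using paired t-tests". The second is between arms: "Between-group differences will be analyzed using one-way ANOVA followed by post hoc" Tukey comparisons. One threshold closes the section and covers both: "The level of significance will be set at p < 0.05". The section does not call the within-arm tests descriptive or supportive, and it does not place them below the ANOVA.

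Other parts of the protocol bear on this:

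- **Hypotheses (Chapter I).** There are eleven: pain, disability, six directions of neck movement, two strength measures and quality of life. Each compares the interventions. None is about change from baseline in one arm.
- **Sample Size Calculation.** The basis is also a between-arm quantity: "A priori power analysis for a repeated measures ANOVA (within-between interaction) was used". The result is 76, raised to 80, or 20 per arm.
- **Intervention Procedures.** All four arms, control included, receive heat, massage and stretching in 18 sessions over 6 weeks, with self-stretching at home.
- **Inclusion Criteria.** Entry requires "Pain intensity of at least 3/10 on the NPRS".
- **Outcome Measures.** Every outcome is measured at baseline and at 6 weeks.

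**The concern.** The study question is whether adding mindful walking, specific neck exercises or both to conventional therapy helps. A paired t-test in one arm compares that arm with its own baseline. The change it tests includes conventional therapy, natural course and non-specific response along with any effect of the added exercise. For pain it may also include regression to the mean, because patients are selected on a minimum pain score. That last argument applies directly to pain only, not to range of motion or strength.

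A significant result in one arm and a non-significant one in another is not evidence that the two arms differ. Significant results in every arm are not evidence that each added exercise works. Both patterns can arise when the added exercises do nothing. With eleven outcomes (quality of life counted once) and four arms there would be 4 × 11 = 44 such p-values. None answers a stated hypothesis, yet each is judged at the same threshold as the tests that do.

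**Working it through.** **1. The plan's own figure.** The protocol uses "an effect size of 0.25, alpha level (α) = 0.05" and power 0.95, and states: "The estimated sample size required was 76 participants". For the group-by-time interaction with k = 4 arms and m = 2 time points, the noncentrality is λ = f²·N·m/(1 − ρ), on 3 and N − 4 degrees of freedom. The correlation ρ is not stated in the text; I assume 0.5, with no sphericity correction.

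- N = 76: λ = 0.0625 × 76 × 2/0.5 = 19.0, power 0.959.
- N = 72: λ = 18.0, power 0.948.

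So 76 is the smallest multiple of 4 that reaches 0.95, and the stated figure reproduces. It sizes the trial for a between-arm effect, not for change within an arm.

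**2. Inputs for the within-arm tests.** From the protocol: four arms, n = 20 each, level 0.05. Assumed: two-sided tests, independent arms, normally distributed changes, and the same true standardised change d (mean change divided by the SD of change) in every arm. The protocol gives no value for d, so a range is shown.

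**3. Formulae.** Let p be the chance that one arm shows a significant improvement, from the noncentral t distribution with 19 degrees of freedom and noncentrality d·√20. Then:

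- all four arms significant: p⁴
- no arm significant: (1 − p)⁴
- some but not all: 1 − p⁴ − (1 − p)⁴

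Example at d = 0.5: p = 0.5645, p⁴ = 0.1015, (1 − p)⁴ = 0.0360, so some but not all = 0.8625.

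**4. Results, n = 20 per arm, true between-arm difference zero throughout.**

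| d | p in one arm | All four significant | Some but not all |
|---|---|---|---|
| 0.3 | 0.2465 | 0.4% | 67% |
| 0.5 | 0.5645 | 10% | 86% |
| 0.6 | 0.7210 | 27% | 72% |
| 0.8 | 0.9239 | 73% | 27% |
| 0.9 | 0.9682 | 88% | 12% |
| 1.0 | 0.9886 | 96% | 4.5% |
| 1.2 | 0.9991 | 99.6% | 0.4% |

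With 19 per arm (76 in total) the last column reads 66%, 87% and 32% at d = 0.3, 0.5 and 0.8, and 6% at 1.0.

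**5. Comparison with a between-arm test.** In 40,000 simulated trials at each of several values of d from 0 to 1.2, with equal true change in all arms, a one-way ANOVA on change was significant in 4.8% to 5.1% of trials, as it should be. At d = 0.5, 81% of trials combined a mixed set of paired t-tests with a non-significant ANOVA.

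**The case against.** The strongest reply is that the randomised comparison is already planned. The sentence after the paired t-tests sets out one-way ANOVA with Tukey, all eleven hypotheses are between arms, and the protocol nowhere says that efficacy will be concluded from within-arm p-values. This stands. A reader might infer that the paired tests are the main analysis or replace the randomised comparison; the documents do not support that. The harm is a possible misreading in the report, not a missing analysis.

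Second, how often the arms disagree depends on a within-arm change that the protocol does not state. With 18 supervised sessions in every arm, a large change everywhere cannot be excluded. This stands too. A reader might infer from the middle of the table that disagreement is likely for every outcome. From about 1.0 SD it falls below 5% per outcome with 20 per arm. Nor can one say without condition both that arms will disagree and that most will be significant. The chance that at least three of four arms are significant is 5% at 0.3 SD, 41% at 0.5, 69% at 0.6 and 97% at 0.8, so the two are likely together only near 0.6.

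Third, the ranking of analyses may be left to a statistical analysis plan that is not shown. That is fair as to a missing label. But the protocol itself names these tests and puts them under the same threshold as the ANOVA, and no hypothesis calls for them.

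**Conclusion.** The point holds as a matter of ranking and interpretation. The protocol fixes within-arm tests at the same 0.05 level as the between-arm ANOVA and does not subordinate them, although no hypothesis is about within-arm change and conventional therapy is common to all arms.

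With equal true change in all arms, the chance of a mixed verdict per outcome is 27% to 86% at the tabulated values from 0.3 to 0.8 SD, and falls to 4.5% at 1.0 and 0.4% at 1.2. At that large end the tests mislead in the other direction: all four arms are significant in 96% of trials at 1.0 SD, with no difference between arms. Neither pattern informs the randomised contrast. These figures rest on independent arms of 20, two-sided tests, normal changes and an assumed standardised change.

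A reader might go further and infer that the paired tests must be deleted. That is more than is needed; labelling them and keeping them out of efficacy conclusions is enough. The change should be made, but because the between-arm test is planned this does not invalidate the design.

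**What to change.** In the Statistical analysis section:

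- Report each arm's mean change with its SD or 95% CI, as description only. If the paired t-tests are kept, label them descriptive and exclude them from any conclusion on efficacy.
- State that treatment conclusions rest only on the between-arm comparison.
- Make that comparison an ANCOVA of the 6-week value adjusted for the baseline value of the same outcome, with Tukey-type adjusted pairwise contrasts. The section does not say whether the planned ANOVA uses the 6-week score or the change, so this also settles the response variable.

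The cost is a few sentences and one covariate in the between-arm model, using baseline values already collected. No visit, measurement, sample size or treatment procedure changes. The downside is that no within-arm p-values would be available to support claims.

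### The only between-group test is a one-way ANOVA with no baseline term and no stated dependent variable; it is valid, but less efficient than ANCOVA on the baseline already collected

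*Protocol*

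**What the plan says.** Protocol, Chapter III:

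- Outcome Measures: "All outcomes will be measured at baseline (pre-intervention) and after 6 weeks (post-intervention").
- Statistical analysis, between groups: "Between-group differences will be analyzed using one-way ANOVA followed by" Tukey's post hoc test. No covariate is named, and the variable entering the ANOVA (6-week value or change) is not given.
- Statistical analysis, within groups: "Within-group comparisons (pre vs post) will be conducted using paired t-tests". This is the only explicit use of the baseline values.
- Sample Size Calculation: "A priori power analysis for a repeated measures ANOVA (within-between interaction) was used", with effect size 0.25, alpha 0.05 and power 0.95. The result is given as "The estimated sample size required was 76 participants", raised to 80 in four arms of 20. No correlation between the two measurements is stated.
- Randomization and Blinding: block randomisation, with no stratification by baseline severity mentioned.

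**The concern.** All eleven hypotheses concern differences between groups, so this one test carries every conclusion of the trial. A one-way ANOVA takes no covariate. If it is run on 6-week values, the baseline plays no part in the comparison. If it is run on change, the baseline enters with a fixed coefficient of 1, which is generally not the best one. In both cases an ANCOVA of the 6-week value on its baseline has residual variance that is no larger, and usually clearly smaller.

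At stake are the width of the confidence intervals in a four-arm trial with 20 patients per arm, and how far each estimate depends on the baseline imbalance that happens to occur. There is also a question of consistency. With two time points, the interaction test used for the sample size is the same as a one-way ANOVA on change, but not the same as one on 6-week values. The analysis section does not say which is meant.

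**Working it through.** **Inputs.** From the protocol: k = 4 groups, m = 2 time points, effect size 0.25 (taken as Cohen's f), alpha 0.05, power 0.95, N = 76 raised to 80, 20 per arm. Assumed: correlation r between baseline and 6 weeks, equal SDs at the two times, a linear relation common to all arms, sphericity correction 1.

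**Step 1: reproduce the 76.** Noncentral F with λ = f²·N·m/(1 − r), df1 = (k − 1)(m − 1) = 3, df2 = (N − k)(m − 1). With r = 0.5 and N = 76, λ = 0.0625 × 76 × 2 / 0.5 = 19, and power is 0.959. At N = 72 it is 0.948, so 76 is the smallest multiple of 4 that reaches 0.95. With r = 0.4 the answer would be 88, and with r = 0.6 it would be 60. So 0.5 is the value implied by the 76, although the protocol does not state it.

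**Step 2: information lost against ANCOVA.** Residual variance relative to that of the 6-week value: 6-week value 1; change 2(1 − r); ANCOVA 1 − r². The share of information lost is therefore r² on 6-week values, and 1 − (1 − r²)/[2(1 − r)] = (1 − r)/2 on change.

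| r | Loss, 6-week values | Loss, change |
|---|---|---|
| 0.3 | 9% | 35% |
| 0.4 | 16% | 30% |
| 0.5 | 25% | 25% |
| 0.6 | 36% | 20% |
| 0.7 | 49% | 15% |
| 0.8 | 64% | 10% |

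At r = 0.5, 80 patients analysed by ANCOVA are worth 80/0.75 ≈ 107 analysed by the planned test.

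**Step 3: power at N = 80.** The planned interaction effect at r = 0.5 corresponds to f² = 0.0625 × 2 / 0.5 = 0.25, that is f = 0.5, on change; because 2(1 − 0.5) = 1, it is also f = 0.5 on 6-week values.

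- Planned effect, one-way ANOVA: λ = 0.25 × 80 = 20, df 3 and 76, power 0.968.
- Planned effect, ANCOVA: λ = 20/0.75 = 26.7, df 3 and 75, power 0.994.
- Smaller effect, f = 0.30 on 6-week values (an assumption made here, not a protocol figure), r = 0.5: λ = 0.09 × 80 = 7.2, power 0.58 on either reading; ANCOVA λ = 7.2/0.75 = 9.6, power 0.72.
- The same f = 0.30 at r = 0.7: 0.58 on 6-week values, 0.82 on change, 0.88 with ANCOVA.

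**Step 4: chance imbalance.** The SD of a baseline difference between two arms of 20 is √(2/20) = 0.32 SD. Given a baseline difference d, the expected error in the estimated effect is r·d on 6-week values, (r − 1)·d on change, and 0 with ANCOVA. For d = 0.32 and r = 0.5 these are +0.16 SD, −0.16 SD and 0. For normal baselines without stratification, a gap above 0.5 SD has probability 11% for a given pair of arms and about 39% for the largest gap among the four arms (the latter by simulation), for each outcome.

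**The case against.** The planned test is not wrong. Under randomisation the unadjusted comparison is unbiased over repeated allocations and does not inflate the type I error through omission of the covariate. On the plan's own effect, with r = 0.5, it already exceeds the 95% power target. The effect f = 0.30 is not in the protocol. The single r = 0.5 is back-calculated, and it is applied to pain, disability, range of motion, strength and quality of life, whose correlations will differ. The dependent variable may be settled in an analysis plan that is not shown. All of this stands, and it limits the point to efficiency and sensitivity to imbalance.

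Three stronger readings are tempting, and the protocol does not support them:

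- A reader might infer that at least a quarter of the information is always lost. That is not a lower bound: the loss is 9% on 6-week values at r = 0.3 and 10% on change at r = 0.8.
- A reader might infer that the baseline is ignored and imbalance left uncorrected. That is true only if 6-week values are analysed, which the protocol does not say. On change scores the baseline is used and imbalance is over-corrected.
- A reader might infer that the trial falls short of its planned power. At the planned effect and r = 0.5 it does not.

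What the objection does not remove is that the protocol fixes the method. One-way ANOVA is a stated choice and has no place for a covariate, whichever variable goes into it.

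**Conclusion.** The point holds as a recommended improvement, not as an error that invalidates the analysis. The size of the loss depends on the correlation and on the variable analysed, and the protocol gives neither; 25% is the figure at the correlation implied by its own sample size. The power gain is small if the planned effect is real and appreciable if the true effect is smaller. These figures rest on equal SDs at the two times and a common linear relation across arms. If the correlation for some outcome were near zero, ANCOVA would gain nothing over 6-week values there and would cost one degree of freedom.

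**What to change.** In the statistical analysis section, replace the one-way ANOVA for each outcome by an ANCOVA of the 6-week value on treatment group (four levels), with that outcome's baseline value as covariate. Report adjusted mean differences between groups with multiplicity-adjusted 95% confidence intervals; these take the place of the Tukey comparisons of unadjusted means. This also settles which variable is analysed. Write it in before any outcome data are seen, so that the adjustment cannot look data-driven.

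The cost is a short text change, one model term and one residual degree of freedom (75 instead of 76 at N = 80). No new data are needed, and the sample size need not change.
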